6.1 Safety Analysis Population

The safety analysis population will include all subjects who have received at least one dose of IMP.

The safety analysis population will be confirmed by Quotient with approval from Genentech after database lock and will be used for the analysis of demographic and baseline characteristics and all safety and palatability data.

6.2 Pharmacokinetic Population

The PK population will include all subjects who have received at least one dose of IMP and who satisfy the following criteria for at least one profile:

- no missing samples or invalid post-dose analytical results at critical time points e.g., around the C_{max}
- no relevant protocol deviations which may impact the study objectives with respect to the PK endpoints
- no relevant AEs such as vomiting which suggest that the whole dose was not available for absorption for a particular subject

The PK population will be confirmed by Quotient with approval from Genentech following derivation of all PK parameter estimates.

All randomized subjects will be used for the PK data listings and the PK population will be used for the provision of PK summary statistics, summary tables and figures.

If required, a PK analysis dataset or datasets may also be documented by Quotient with approval from Genentech at the same time as the PK population. The PK analysis dataset(s) will be a subset of the PK population. Individual subject profiles (i.e., periods) will be excluded from the PK analysis dataset where deemed appropriate such as if the subject in the study period affected did not meet the bullet point criteria above or other study emergent point related to PK analysis or interpretation.

The PK analysis dataset(s) may be used to generate additional summary tables and figures for the PK concentration and PK parameter data and may be used for the formal statistical analysis of the PK parameter data. Requirements for additional summary tables and figures will be documented at the same time as the PK population.

7 Subject Disposition, Demographics and Baseline Characteristics

No formal statistical testing will be performed on subject disposition or on demographic or baseline data. All data will be listed for all randomized subjects. Summaries of subject disposition and analysis populations will be based on all randomized subjects and summaries of all other data described in this section will be based on the safety population, unless otherwise stated.

Separate summary tables and listings will be produced for each study part.

7.1 Screening Failures

Data for subjects who have failed screening will be databased but will not be cleaned and therefore will not be included in the SDTM or ADaM datasets or any of the tables, figures or data listings.

7.2 Subject Disposition and Withdrawals

The number and percentage of subjects randomized, dosed, completed and discontinued will be presented by treatment sequence and overall. If any subjects discontinued from the study early, then the number of subjects for each reason for discontinuation will be presented by treatment sequence and overall. However, if none of the subjects discontinued from the study early, then the reasons for discontinuation will not be populated in the summary table.

Subject disposition and withdrawal data will be listed, including details of informed consent.

Protocol deviations and any violations of the inclusion/exclusion criteria will also be listed.

7.3 Analysis Populations

A summary table will be produced detailing the number and percentage of subjects in the safety and PK populations for each treatment sequence and overall. The reasons for exclusion from each population will also be included in the summary.

Details of subjects included and excluded in the different analysis populations will be listed.

7.4 Analysis Datasets

If applicable, a summary table will be produced detailing the number and percentage of subjects in each analysis dataset (i.e., PK) for each treatment. The table will be based on the relevant population the dataset is a subset of (i.e., the PK population). The reasons for exclusion from each dataset will also be included in the summary.

Details of subjects included and excluded in the different analysis datasets will be listed.

7.5 Demographic Characteristics and Lifestyle Details

Demographic data (date of birth, ethnicity, race, sex, height [cm], weight [kg] and body mass index [BMI; kg/m²]) will be recorded at screening. Age will be calculated using the following formula:

$$\text{Age(years)} = \frac{\text{Date of first dose of IMP} - \text{date of birth}}{365.25}$$

and will be rounded down to the nearest year (using the SAS Software floor function). If any subjects are randomized but not dosed and had other assessments recorded, age will be calculated using the date of informed consent.

Summary statistics (mean, standard deviation [SD], median, minimum, maximum and number of subjects with an observation [n]) will be presented for age, height, weight and BMI at screening by treatment sequence and overall. The number and percentage of subjects will be presented by treatment sequence and overall for ethnicity, race and sex. The denominator for the percentage is all subjects in the safety analysis population. If any values are missing, a "missing" row will be presented on the table.

Lifestyle details (i.e., smoking history [does the subject smoke, use e-cigarettes or use nicotine replacement products?] and alcohol consumption) will be summarized by treatment sequence and overall as a categorical variable.

Demographic and lifestyle data will be listed.

7.6 Medical/Surgical History

Medical/surgical history will be recorded for each subject at the screening visit and will be coded using the Medical Dictionary for Regulatory Activities (MedDRA v22.0 or most recent version). All medical/surgical history data will be listed by subject, MedDRA system organ class (SOC) and preferred term (PT).

7.7 Prior and Concomitant Medication

Medications (product name) will be coded using the World Health Organization (WHO) Drug Dictionary Global Drug Reference: 2019 Q1 version (or more recent version), using the following Anatomical Therapeutic Chemical (ATC) classification codes:

- product name (Medication)
- preferred name
- drug code
- therapeutic subgroup (ATC 2nd level name and code)
- chemical subgroup (ATC 4th level name and code)

Prior medications are defined as medications that start and stop prior to the first dose of IMP. All other medications will be defined as concomitant medications including those that start prior to the first dose of IMP and continue thereafter. Any medications with an unknown start or stop date will be assumed to be concomitant medications unless a partial start or stop date indicates otherwise.

All medications, including coded terms, and the underlying indication for which the medication was given, will be listed. One combined data listing of prior and concomitant medications will be provided. All prior medications as defined above will be flagged with a "#" symbol. Within this flagged group, medications that started after screening and stopped before dosing of IMP will also be flagged using a "*" symbol.

7.8 Other Baseline Characteristics

All other baseline characteristics, as listed below, at screening and on Day -1 (unless otherwise stated) for each period (as appropriate) will be listed:

- urine drug screen
- alcohol and carbon monoxide breath test

- virology (screening only)
- serum pregnancy test (screening only) and urine pregnancy test (Day -1 of each period only) for female subjects
- follicle stimulating hormone (FSH) test for post-menopausal female subjects (screening only)

8 Efficacy

Not applicable for this Phase I study.

9 Pharmacokinetics

9.1 Pharmacokinetic Parameter Estimation

Where concentrations are provided as ng/mL by the bioanalytical provider for entrectinib and M5, these will be converted in SAS to nmol/L for the calculation of PK parameters, as below:

Entrectinib

Concentration (nmol/L) = concentration (ng/mL) / molecular weight entrectinib (560.65)

M5

Concentration (nmol/L) = concentration (ng/mL) / molecular weight M5 (546.62)

The PK parameters for entrectinib and M5 in plasma will be estimated where possible and appropriate for each subject and treatment by non-compartmental analysis methods using Phoenix WinNonlin software (v8.0 or a more recent version, Certara USA, Inc., USA).

9.1.1 Definition of Pharmacokinetic Parameters

Plasma PK parameter definitions are provided in [Table 4](#).

Table 4 Plasma Pharmacokinetic Parameters and Rounding Specifications

Parameter	Definition	Unit	DP or SF	No. of DP/SF
Tmax	Time of maximum observed concentration	h	DP	2
Cmax	Maximum observed concentration	nmol/L	SF	3
AUC0-t	Area under the curve from 0 time to the last measurable concentration	nmol.h/L	SF	3
AUC0-inf	Area under the curve from 0 time extrapolated to infinity	nmol.h/L	SF	3
%AUCextrap	Percentage of AUC0-inf extrapolated beyond the last measurable concentration	%	DP	2
T1/2	Apparent elimination half-life	h	DP	2
Lambda-z	Slope of the apparent elimination phase	1/h	DP	4
CL/F	Apparent total body clearance calculated after a single extravascular administration where F (fraction of dose	mL/min	SF	3

Parameter	Definition	Unit	DP or SF	No. of DP/SF
	bioavailable) is unknown			
Vz/F	Apparent volume of distribution based on the terminal phase calculated after a single extravascular administration where F (fraction of dose absorbed) is unknown	L	SF	3
Frel AUC0-t	Relative bioavailability based on AUC0-t	%	DP	2
Frel AUC0-inf	Relative bioavailability based on AUC0-inf	%	DP	2
MPR AUC0-inf	Metabolite to parent ratio based on AUC0-inf	NA	DP	2
Lambda-z Lower*	Lower limit on time for values to be included in the calculation of Lambda-z	h	DP	2
Lambda-z Upper*	Upper limit on time for values to be included in the calculation of Lambda-z	h	DP	2

DP=decimal places

SF=significant figures

*=these values should be listed but omitted from the descriptive statistics

NA=not applicable

9.1.2 Rules for Pharmacokinetic Parameter Estimation

The imputation of non-numerical or negative values reported in the input dataset will be performed as follows:

- pre-dose sample times will be entered as zero
- values that are below the limit of quantification (BLQ) obtained prior to the C_{max} will be entered as zero
- values that are BLQ after the C_{max} will be treated as missing
- should partial AUCs be required then values that are BLQ after C_{max} may be imputed as zero for these partial areas if λ_z cannot be determined
- values that are quantifiable after at least 2 consecutive BLQ values after C_{max} will be treated as missing for the calculation of PK parameters
- values that are reported as "No Result" (NR) or "No Sample" (NS) etc. will be treated as missing

PK parameters will be estimated using standard Phoenix WinNonlin methods, details of which may be found in the documentation accompanying the WinNonlin software package. The following constraints will apply:

Parameter Estimation	Constraint
Sampling times	Actual
Trapezoidal method	Lin up log down etc.
Number of points used for λ_z	At least 3, not including C_{max}
Minimum requirements for AUC	At least 3 consecutive quantifiable concentrations
Dose	Nominal
Rounded dose level	0 Decimal Places

Where possible, the terminal elimination rate constant (λ_z) will be calculated for all subjects. The value of λ_z will be determined by the slope of the regression line of the natural log transformed concentrations vs time.

The choice of data points for determination of λ_z will be reviewed by the pharmacokineticist who may adjust the selection in order to provide a more appropriate fit. The choice of data points for determination of λ_z for each profile will be confirmed following a documented peer review.

Relative bioavailability (Frel) will be calculated as follows:

$$F_{rel} = \left\{ \frac{AUC \text{ (test)}}{AUC \text{ (reference)}} \right\} \times 100$$

Frel will be calculated using AUC_{0-t} and AUC_{0-inf} . If for any reason the AUC_{0-inf} is not calculable then an alternative AUC over a partial area may be used.

The following comparisons will be made:

Part 1

- 600 mg F15 vs 600 mg F06
- 600 mg F16 vs 600 mg F06

Part 2

- 200 mg F06 coarse vs 200 mg F06 fine

Metabolite to parent ratios (MPR) after a single dose administration will be calculated as follows using AUC_{0-inf} . If for any reason the AUC_{0-inf} is not calculable then an alternative AUC such as AUC_{0-t} or AUC over a partial area may be used:

$$MPR = \frac{AUC \text{ (metabolite)}}{AUC \text{ (parent)}}$$

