3.1 Responsibilities

The Data Sciences Department at Quotient will be responsible for the production of the following items using Quotient SOPs: CDISC study data tabulation model (SDTM) and analysis data model (ADaM) datasets; PK parameter estimation and output and safety and palatability output; including all summary tables, figures and data listings, and formal statistical analysis; and the clinical study report (CSR).

Quotient will provide three sets of tables, data listings and figures during the study:

- after database close but prior to database lock for Genentech, Inc. (Genentech) review (safety and palatability tables and listings only)
- post database lock TFLs (draft) for Genentech review and
- post-review TFLs (final) for inclusion into the CSR.

Quotient will be responsible for the quality control (QC) of all deliverables prior to the client review ([Section 14.2](#)).

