5.3 Randomization (Including Replacement Subjects)

Part 1

Using a computer-generated randomization schedule, subject numbers will be allocated to one of three treatment sequences ([Table 2](#)) in Part 1. The allocation will be balanced with 5 subjects assigned to each of the treatment sequences.

Table 2 Part 1 Treatment Sequences

Treatment Sequence	Period 1	Period 2	Period 3
T1T2R	Test formulation 1	Test formulation 2	Reference formulation
T2RT1	Test formulation 2	Reference formulation	Test formulation 1
RT1T2	Reference formulation	Test formulation 1	Test formulation 2

T1; Test formulation 1 = Multi-particulate formulation 1: Entrectinib film-coated mini-tablets, 600 mg (240 x 2.5 mg) (Ro 710-2122/F15)

T2; Test formulation 2 = Multi-particulate formulation 2: Entrectinib film-coated mini-tablets, 600 mg (240 x 2.5 mg) (Ro 710-2122/F16)

R; reference formulation = F06 capsule formulation: Entrectinib (RXDX-101) F06 hard capsules, 600 mg (3 x 200 mg) (Ro 710-2122/F04)

Eligible subjects will be assigned a unique identification number on the morning of dosing in Period 1 according to the code █ to █ for Part 1, using the lowest number available. Replacement subjects will be allocated subject numbers █ to █, where the last 2 digits are the same as those of the original subject (e.g., if Subject █ withdraws the replacement will have Subject Number █). Replacement subjects will be assigned to the same treatment sequence as the subject they replaced.

A treatment allocation list will be produced prior to dosing using the randomization schedule and will be retained in the Investigator Site File (ISF).

The original randomization schedule and proof of quality control procedures will be held by the Data Sciences department at Quotient Sciences until the study is archived, at which time the randomization materials will be retained in the ISF.

Part 2

Using a computer-generated randomization schedule, subject numbers will be allocated to a treatment sequence ([Table 3](#)) in a 1:1 ratio in Part 2. The allocation will be balanced with 8 subjects assigned to each treatment sequence.

Table 3 Part 2 Treatment Sequences

Treatment Sequence	Period 1	Period 2
TR	Test formulation	Reference formulation
RT	Reference formulation	Test formulation

T = Test formulation; Entrectinib F06 HPMC Capsules (coarse API), 200 mg

R = Reference formulation; Entrectinib (RXDX-101) F06 hard capsules, 200 mg (fine API) (Ro 710-2122/F04)

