5.4 Blinding Issues

This is an open-label study and therefore blinding is not required.

6 Populations for Analysis

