9.2 Pharmacokinetic Parameter Reporting Specifications

The following parameters will be reported for each study part as applicable, according to the rounding specifications provided in [Table 4](#):

Study Parts 1 and 2:

t_{max} , C_{max} , AUC_{0-t} , AUC_{0-inf} , %AUCextrap, $t_{1/2}$, λ_z , λ_z Lower, λ_z Upper, CL/F, V_z/F , MPR (based on AUC_{0-inf}) and Frel (based on AUC_{0-t} and AUC_{0-inf}).

The following flags/footnotes may be applied to the PK parameters:

Flag	Footnote
a	Rsq of regression was <0.9
b	Period used for regression analysis was less than 2-fold the calculated half-life
c	Extrapolated portion of AUC_{0-inf} >20%

d	Insufficient post- C_{max} data points for estimation of λ_z
e	Entire profile BLQ, no PK parameters could be calculated
f	Quantifiable pre-dose values were observed, however were considered less than 5% of C_{max}

In the event that the R-squared (Rsq) of regression was <0.9 ("a" flag) or the extrapolated portion of $AUC_{0-\infty}$ >20% ("c" flag), then the parameter estimates derived using λ_z and/or $AUC_{0-\infty}$ will be deemed unreliable and will be listed but excluded from the summary statistics and formal statistical analysis.

In the event that the period used for regression analysis was less than 2-fold the calculated half-life ("b" flag) parameter estimates derived using λ_z will be listed, flagged and included in summary statistics and formal statistical analysis.

In the event that quantifiable pre-dose values less than 5% of C_{max} were observed ("f" flag), all parameter estimates for the profiles affected will be listed, flagged and included in summary statistics and formal statistical analysis.

In the event that quantifiable pre-dose concentrations greater than 5% of C_{max} are observed, requirements for further action will be agreed with Genentech and documented at the same time as the PK population.

Additional flags may be applied based on emerging data.

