9.2.4 Statistical Analysis of Pharmacokinetic Parameters

Formal statistical analysis will be performed on the entrectinib and M5 PK parameters C_{max} , AUC_{0-t} and AUC_{0-inf} to assess the relative bioavailability between test and reference formulations. The PK parameters will undergo a natural logarithmic transformation and will be analysed using mixed effect modelling techniques. The model will include terms for treatment, period and sequence fitted as fixed effects and subject nested within sequence fitted as a random effect.

The following pairwise treatment comparisons (*test versus reference*) are of interest in Part 1:

- 600 mg F15 vs 600 mg F06
- 600 mg F16 vs 600 mg F06

The following pairwise treatment comparison (*test versus reference*) is of interest in Part 2:

- 200 mg F06 coarse vs 200 mg F06 fine

If the number of subjects with reliable estimates of AUC_{0-inf} for any period falls below the planned number of evaluable subjects, then consideration will be given as to whether formal statistical analysis will be performed.

The adjusted means including differences from the pairwise comparisons listed above and their associated 90% CIs obtained from the model will be back transformed on the log scale to obtain adjusted GMRs and 90% CIs of the ratios, where the ratio, defined as

test/reference, will be presented. In addition, these will be presented together with the p-value from the pairwise treatment comparison and the intra-subject variability values (denoted as CVw in the results table), where the null hypothesis is defined as no treatment difference.

The intra-subject variability values will be calculated for all treatments combined and are obtained from the residual term from the SAS Software output. These values are calculated as follows:

$$CVw = 100 \times [\exp(\text{Mean Square Error}) - 1]^{1/2}$$

The ANOVA table from the model with F-statistic and p-value for the fixed effects will be presented on a separate page.

The statistical analysis will be performed using actual treatment received and planned sequence as detailed on the randomization schedule. The model will be fitted using the SAS Software procedure PROC MIXED, the method will be specified as Restricted Maximum Likelihood and the denominator degrees of freedom for the fixed effects will be calculated using Kenward and Roger's method [1]. The following is an example of the SAS Software code that will be used:

```

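### Lambda-z points may be adjusted by judgement with no stated masking, and for AUC0-inf the choice affects both the value and its inclusion; selecting and locking points on coded profiles is a cheap, optional improvement

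*SAP*

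**What the plan says.** SAP 9.1.2 estimates PK parameters with standard WinNonlin methods. The regression for lambda-z needs "At least 3, not including" Cmax. The selection of points "will be reviewed by the pharmacokineticist who may adjust the selection in order to provide a more appropriate fit", and the choice "for each profile will be confirmed following a documented peer review".

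SAP 9.2 sets the consequence. If R-squared is below 0.9, or more than 20% of AUC0-inf is extrapolated, the estimates that use lambda-z or AUC0-inf "will be deemed unreliable and will be listed but excluded from the summary statistics and formal statistical analysis". A regression window shorter than two half-lives is flagged but kept.

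SAP 9.2.4 says "Formal statistical analysis will be performed on the entrectinib and M5 PK parameters" Cmax, AUC0-t and AUC0-inf. Protocol 6.5 names Cmax and AUC0-inf of both analytes as the primary parameters.

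On masking, SAP 5.4 says only: "This is an open-label study and therefore blinding is not required". SAP 3.1 makes Quotient's Data Sciences Department responsible for "PK parameter estimation and output and safety and palatability output". SAP 5.3 says the original randomization schedule "will be held by the Data Sciences department at Quotient Sciences until the study is archived".

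**The concern.** The aim of a more suitable fit is not defined, so two competent analysts could choose different windows for the same profile. One choice feeds two things: the extrapolated area, and the two statistics that admit or exclude the AUC0-inf value. If the analyst knows which profile is test and which is reference, expectation can influence both. The AUC0-inf model has no means of detecting this. The sensitivity analyses in SAP 9.2.4 deal with distributional assumptions, not with the choice of points.

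Open-label dosing explains why subjects and site staff are not blinded. It does not explain why treatment labels should be available when points are chosen for a primary parameter.

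**Working it through.** **Inputs from the documents.** Entrectinib half-life 20 to 30 h and tmax about 4 h (Protocol 1.1.2.2); last sample at 96 h (Protocol Appendix 2); within-subject CV of AUC0-inf 20%, 12 evaluable subjects, CI bounds within 1.25x of the estimate (Protocol 6.1).

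**Assumptions.** A one-compartment oral curve, also tried with a faster second phase; log-normal residual error of 5 to 20%; M5 half-life of 40 or 50 h. The documents give neither the residual error nor the M5 half-life. The 20% CV in Protocol 6.1 is for AUC0-inf, not for scatter about the terminal line.

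**1. The plan's own precision.** The CI factor is exp(t × s_w × √(2/n)), with s_w = √ln(1 + 0.20²) = 0.198.
- Part 2 (10 df): exp(1.812 × 0.198 × 0.408) = 1.158.
- Part 1 (20 df): exp(1.725 × 0.198 × 0.408) = 1.150.

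Both are within 1.25x, so the stated figure is reproduced. The half-width for comparison is about 15%.

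**2. Extrapolated share at 96 h.** It is 3.75% at a half-life of 20 h, 7.2% at 25 h and 11.15% at 30 h. It reaches 20% only at about 41 h.

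**3. Sensitivity to lambda-z.** A lambda-z 20% too low raises AUC0-inf by share × (1/0.8 − 1) = share × 0.25. That is 3.75 × 0.25 = 0.9% at 20 h and 11.15 × 0.25 = 2.8% at 30 h. The share itself becomes 4.6% and 13.6%, so the 20% flag is not reached.

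**4. Worst-case picking of values.** Profiles were simulated on the protocol's sampling times. The largest admissible AUC0-inf was taken for every test profile and the smallest for every reference profile.

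| Half-life | Bias in AUC0-inf ratio (5–15% error) | Profiles whose inclusion depends on the window |
|---|---|---|
| 20 h | 0.2–0.5% | 0–1.4% |
| 30 h | 0.7–2.1% | 0–1.6% at 5–10% error; about 14% at 15% |
| 40 h (assumed, M5) | 1.2–2.6% | 18–44% |
| 50 h (assumed, M5) | 0.4–1.7% | 0.4–26% |

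At 50 h most profiles exceed 20% extrapolation even with the best-fitting window.

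**5. Inclusion also steered.** Let p be the share of profiles that can be moved in or out. In the extreme case, the movable test profiles below average are dropped, and so are the movable reference profiles above average. Half of p goes from each treatment. The dropped values lie on average 0.798 × 0.198 = 0.158 from the mean on the log scale, so the log ratio shifts by 2 × (p/2) × 0.158/(1 − p/2). Choosing among the last 3, 4 or 5 points at 30 h, p is 13% at 15% error and 24% at 20% error; value picking within those windows adds up to 1.5%.
- 15% error: 2 × 0.065 × 0.158/0.935 + 0.015 = 0.037, about 4%.
- 20% error: 2 × 0.12 × 0.158/0.88 + 0.015 = 0.058, about 6%.

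Simulating this rule, which also lets residual error move AUC0-inf itself, gives about 4% and 7%. Over 20 to 30 h and 5 to 20% error the range is 0.1 to 7%. Windows reaching further back would allow somewhat more.

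**6. Effect of masking on precision.** None. Planned N and the factors in step 1 are unchanged.

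**The case against.** A reader might infer that points are routinely re-picked by hand by someone who can see the treatment, and that this decides whether the profile enters the primary analysis. The documents do not support that. Adjustment is permitted, not routine. Sight of treatment is an inference from the open-label design and the shared department; holding the original schedule does not mean the pharmacokineticist works from it. The flags remove only estimates that use lambda-z or AUC0-inf. Cmax, the other primary parameter, and AUC0-t remain.

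The plan also has real safeguards. Each profile's selection is peer-reviewed, the lower and upper limits of the regression window are listed, and excluded estimates are listed too, so any profile can be refitted. AUC0-t gets the same model, ratio and 90% CI, so a strongly steered AUC0-inf ratio should stand apart from it. The objectives are exploratory, and the 80 to 125% lines are illustrative.

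Most of this stands and lowers the severity. Two parts do not fully answer the point. Peer review is not said to be masked, and listings make a choice traceable without preventing it. A ceiling near 2% counts only the values chosen; it leaves out selective exclusion.

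**Conclusion.** The point holds in a limited form. A judgement-based step with no stated masking affects the value of one primary parameter, AUC0-inf, and whether it is analysed. For entrectinib the worst case is about 2% or less from value picking. With inclusion steered as well, it is about 4 to 7% at a 30 h half-life and 15 to 20% residual error. Both are extremes, with every choice pushed in opposite directions by treatment, and both are well inside a CI half-width of about 15%. Realistic bias is small.

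For M5 it could be larger if the half-life is near 40 h or more, close to where extrapolation crosses 20%; the documents do not allow this to be checked. The sizes rest on the assumed curve, residual error and M5 half-life. Nothing here shows that the ratio is biased or that the stated precision fails. Severity: optional.

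**What to change.** In SAP 9.1.2, state that:
- point selection and its peer review are done on profiles with treatment, period and sequence replaced by dummy codes; a subject's profiles may still be viewed side by side;
- selection starts from the WinNonlin default, and every change has a recorded reason;
- the selection is locked before treatment codes are merged.

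In SAP 5.4, limit the statement on blinding to the clinical phase. In SAP 9.2.4, add AUC0-inf under the default selection as a sensitivity analysis.

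The cost is one recoding step, a few SAP sentences, one extra model run and a short delay before codes are merged. Masking removes only treatment-dependent picking. Exclusions caused by a truly long half-life or a poor fit remain. So do the confirmation of the PK population after parameters are derived (SAP 6.2) and the discretion over whether to analyse AUC0-inf when reliable estimates are few (SAP 9.2.4).
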